#### 14.8.2 Medical Monitor Review

The DAIT/NIAID Medical Monitor shall receive at least monthly reports from the SACCC compiling new and accumulating information on AEs, SAEs, and pregnancies recorded by the study site(s) on appropriate eCRFs.

In addition, the Medical Monitor shall review and make decisions on the disposition of the SAE and pregnancy reports received from the site investigator via the SACCC (See Sections 14.5 and 14.6).

#### 14.8.3 DSMB Review

The DSMB shall review safety data at least yearly during planned DSMB Data Review Meetings. Data for the planned safety reviews will include, at a minimum, a listing of all reported adverse and SAEs.

The DSMB will be informed of an Expedited Safety Report in a timely manner.

Confidential Page 62 of 80

In addition to the pre-scheduled data reviews and planned safety monitoring, the DSMB may be called upon for *ad hoc* reviews. The DSMB will review any event that potentially impacts safety at the request of the PI or DAIT/NIAID. Please see *Section 5.4 Dose Escalation Plan/Toxicity Management*.

Confidential Page 63 of 80

### 15. Statistical Considerations and Analytical Plan

#### 15.1 Overview

The objectives of this multi-center, open-label, pilot dose-escalation study are described in *Section 3. Study Design*. Briefly, they are to evaluate the safety, tolerability, DLTs and biological activity of ex vivo-expanded darTregs in combination with lymphocyte depletion using Thymoglobulin° and TAC- or EVR-based Treg-supportive IS in adult liver transplant recipients.

#### 15.2 Outcomes

The study design as well as the safety, clinical, and mechanistic outcomes are described in Section 3.

#### 15.3 Measures to Minimize Bias

Although the study is open-label, the mechanistic analyses of recipient specimens at the central laboratories will be blinded with respect to the status of the recipient in the study. Subjects who do not receive Thymoglobulin® or subjects who receive Thymoglobulin®, but do not subsequently receive darTregs will be replaced according section 13.3.

# 15.4 Analysis Plan

Statistical analyses of the safety and clinical outcomes will be descriptive, employing standard methods for the estimation of person-week incidence rates and their exact two-sided 95% confidence intervals. Statistical analyses of the mechanistic outcomes will be exploratory in nature. The plans for statistical analyses of study data will be described in more detail in a Statistical Analysis Plan (SAP).

### 15.4.1 Analysis Samples

The Safety Sample will be comprised of all study subjects who are consented and receive any study therapy, including leukapheresis, T cell depletion followed by TAC- or EVR-based Treg-supportive IS and darTreg infusion. This excludes consented subjects who were terminated before receiving any study treatment.

Safety and clinical outcomes will be analyzed within the Safety Sample as a whole and within the following two treatment-related analysis periods during which:

- Subjects receive any Thymoglobulin°, followed by TAC- or EVR-based darTreg supportive IS
- Subjects receive darTreg infusions at any dose.

Subjects will contribute AEs and weeks at risk to each analysis period for as long as they are on the corresponding study treatment in that analysis period. Thus, if they progress from T cell depletion to darTreg infusion at any dose, they will contribute subsequent AEs and weeks at risk to the darTreg infusion analysis period when they initiate any darTreg infusion and that will continue until the end of their follow-up time on study.

In addition, a third subset of the safety sample will include any enrolled subject who has PBMCs collected for darTreg manufacturing (phlebotomy or leukapheresis) and may or may not receive subsequent Thymoglobulin®, darTreg supportive IS or darTreg infusions.

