#### 3.2 Safety Outcomes

The safety, tolerability, and ties of darTreg therapy given within the context of either a TAC- or EVR-based IS regimen will be evaluated with the rate of the following events within 40 weeks of transplantation:

Clinical outcomes that will be described are:

- 1. Incidence and severity of biopsy-proven AR and/or CR (Demetris A. J., 1997) (Demetris A. D., 2000)
- 2. Incidence of ≥ Grade 3 infections as defined in Section 14.3.1
- 3. Incidence of wound complications (≥ CTCAE Grade 3)

Confidential Page 30 of 80

- 4. Incidence of anemia, neutropenia, and/or thrombocytopenia (according to study defined reporting requirements, *Section 14.3.1*)
- 5. Incidence of AEs attributable to the darTreg infusion including infusion reaction / cytokine release syndrome (CRS) (≥ CTCAE Grade 3), and malignant cellular transformation.

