### 7. Premature Discontinuation of Investigational Therapy

# 7.1 Premature Discontinuation of Thymoglobulin and/or Treg Supportive IS Regimen

Study IS regimen may be prematurely discontinued for any participant for any of the following reasons:

- 1. Inability to tolerate at least 3 mg/kg Thymoglobulin® or inability to deplete CD3 count to less than or equal to 50μ/L (50/mcL) or total lymphocyte count to less than equal to 0.1 x 109/L after study Thymoglobulin® administration
- 2. Inability to tolerate TAC- or EVR-based maintenance IS
- 3. The diagnosis of severe AR (Banff criteria) at any time after transplantation
- 4. The diagnosis of early or late CR (Banff criteria) at any time after transplantation
- 5. The occurrence of steroid refractory rejection at any time after transplantation
- 6. Poor compliance with study procedures.
- 7. Investigator decision that the study IS regimen and/or future study treatment is no longer in the best interest of the participant.
- 8. Failure to manufacture and supply the cellular product two times for the same subject

There are a myriad of diagnoses that might lead an investigator to determine that the study IS regimen and/or darTreg infusion is no longer in the best interest of the participant. While there are likely an infinite number of specific reasons, general reasons include severe, life-threatening infections, malignancy (excluding skin cancer), GvHD, pneumonitis, severe renal dysfunction / proteinuria, serious medical co-morbidity such as myocardial infarction, and logistical issues including patient relocation and record of non-compliance.

The (Data Safety Monitoring Board) DSMB will be provided with information about cases of premature discontinuation occurring in any stage. Subjects who have prematurely discontinued the study regimen will enter into a schedule of events (SOE) of reduced monitoring intensity for purpose of safety (Please refer to Section 13.4 and Safety Follow-Up SOE)

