#### 13.4 Follow-up after Early Study Withdrawal

# 13.4.1 Follow-up after Premature Discontinuation from Stage 1

Subjects who are prematurely withdrawn from Stage 1 of the study will be terminated from the study and will not be followed. Subjects who move to Stage 2 but discontinue from the trial prior to receiving study directed Thymoglobulin will not be followed.

# 13.4.2 Follow-up after Premature Discontinuation from Stage 2 or Stage 3

All subjects who are prematurely withdrawn from Stage 2 and have received any study directed Thymoglobulin® (without receiving darTregs) will have a safety follow up visit 4 weeks after stopping study therapy (Appendix 4). In addition, these subjects will continue the safety follow up schedule (Appendix 4) until 40 weeks after transplantation. Subjects prematurely discontinuing study therapy from Stage 3 after receiving any part of a darTreg infusion will be followed according to Appendix 5 starting with a follow up visit within 4 weeks after the decision to stop study therapy.

Confidential Page 56 of 80

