### 14.4 Collection and Recording of Adverse Events

#### 14.4.1 Collection Period

During Stage 1, AEs will be collected from the time of first study procedure (leukapheresis or 450-500 ml blood draw), until 72 hours after completion of the leukapheresis procedure or 450-500 ml blood draw. AEs occurring outside the 72 hour window should be reported if the investigator deems a possible association with the protocol mandated leukapheresis or blood draw.

During Stages 2 and 3 (including Cohort 1 follow up), AEs will be collected from the time of first Thymoglobulin® administration, until a subject completes study participation or until 30 days after he/she prematurely withdraws (without withdrawing consent) or is withdrawn from the study.

Additionally, elevated liver tests (i.e. ALT, AST, ALP, GGT, and bilirubin) must be reported starting 7 days after transplant. Events involving unexpected elevations of liver tests in the first week should be reported according the site investigator's judgment.

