5. ANALYSIS SAMPLES

The Safety Sample will be comprised of all study subjects who are consented and receive any study therapy, including leukapheresis, Treg-supportive IS and darTreg infusion. This excludes consented subjects who were terminated before receiving any study treatment.

Safety and clinical outcomes will be analyzed within the Safety Sample as a whole and within the following two treatment-related analysis periods during which:

- Subjects receive any darTreg supportive IS
- Subjects receive darTreg infusions at any dose.

Subjects will contribute adverse events and weeks at risk to each analysis period for as long as they are on the corresponding study treatment in that analysis period. Thus, if they progress from darTreg supportive IS to darTreg infusions at any dose, they will contribute subsequent adverse events and weeks at risk to the darTreg infusion analysis period when they initiate any darTreg infusion and that will continue until the end of their follow-up time on study.

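### The Treg-supportive IS period rate drops events and weeks after the regimen stops, although the outcome runs to week 40, and the protocol conflicts on how long adverse events are collected

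*Protocol*

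**What the plan says.** Protocol 3.2 sets the time frame: safety "will be evaluated with the rate of the following events within 40 weeks of transplantation". SAP 2.1 uses the same 40 weeks.

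Protocol 15.4.1 then defines two analysis periods, one for Thymoglobulin and Treg-supportive IS and one for darTreg infusion. Its general rule is "Subjects will contribute AEs and weeks at risk to each analysis period for as long as they are on the corresponding study treatment". SAP section 5 has the same rule: "Subjects will contribute adverse events and weeks at risk to each analysis period for as long as they are on the corresponding study treatment". For subjects who go on to infusion, 15.4.1 adds that they contribute to the darTreg period and "that will continue until the end of their follow-up time on study". Outcomes are also analysed in the Safety Sample as a whole, with no on-treatment limit stated for that analysis.

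Protocol 7.1 lists reasons for which the regimen may be stopped. One is "The diagnosis of severe AR (Banff criteria) at any time after transplantation"; chronic rejection and steroid-refractory rejection are others, and severe infection is named as a general reason.

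On adverse event (AE) collection in Stages 2 and 3, Protocol 14.4.1 runs "until a subject completes study participation or until 30 days after he/she prematurely withdraws" or is withdrawn by others. Section 14.4.4 puts the same 30-day limit on following recorded events. For subjects who leave Stage 2 after any Thymoglobulin, however, 13.4.2 says that "these subjects will continue the safety follow up schedule (Appendix 4) until 40 weeks after transplantation". The tables in Appendices 4 and 5 carry rows for AE assessment and rejection episodes through week 40.

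Protocol 15.4.3 and SAP 8.1 plan no sensitivity analyses, and SAP 9.1 does not impute missing safety data.

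**The concern.** The reasons for stopping overlap with the outcomes being estimated. A subject taken off the regimen for rejection or severe infection leaves both the numerator and the risk set of the IS period at that moment. If never infused, the subject does not enter the darTreg period either. If such subjects have more events afterwards than those who stay on the regimen, the IS period rate understates what happens over 40 weeks to patients started on it.

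The stopping-rule text takes the broader view: Protocol 14.8.1 has every patient who receives any Thymoglobulin contribute to the safety assessment of the regimen, with no on-treatment limit.

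The collection conflict adds a second problem. If a site follows 14.4.1 and stops recording after 30 days, the later events do not exist in the database. Neither the whole-sample analysis nor the Stage 2 stopping rule can then use them.

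**Working it through.** **1. The plan's own figures.** Protocol 15.6 gives the planned person-weeks, and they reproduce:

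- 18 subjects × 12 weeks = 216
- 12 × 28 = 336 (darTreg period)
- 6 × 40 + 12 × 12 = 384 (IS period, with Cohort 1 followed to week 40)

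All 30 rows of Table 8 reproduce to four decimals as exact Poisson limits. For example, 4 events in 384 person-weeks give 0.0104 (0.0028 to 0.0267). The table assumes complete follow-up, with nobody leaving early, so it neither shows nor excludes the problem.

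**2. Where a subject's time goes.** Take a Stage 2 subject who stops the regimen at week 6 (an assumed time) and is never infused:

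| Rule | Weeks counted | Weeks omitted of 40 |
|---|---|---|
| On treatment (15.4.1, SAP 5) | 6 | 34 |
| Plus 30 days (14.4.1) | 6 + 30/7 = 10.3 | 29.7 |
| To week 40 (3.2, 13.4.2, Appendix 4) | 40 | 0 |

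The first row is what enters the IS period rate. The second and third rows are the two competing limits on what can be recorded, and so on what the whole-sample analysis can contain.

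**3. Effect on the IS period rate.** The documents give neither the number who will stop nor their later event rate, so this is an illustration. Assume that four subjects stop at week 6, are never infused, and are replaced under Protocol 13.3, so that they come on top of the planned 384 person-weeks.

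- On-treatment person-weeks: 384 + 4 × 6 = 408
- Full person-weeks: 384 + 4 × 40 = 544
- Lost: 544 − 408 = 136, and 136/544 = 25%

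Let the on-treatment event rate be λ and the rate after stopping be rλ. The full rate relative to the reported one is

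(408λ + 136rλ) / 544λ = 0.75 + 0.25r

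- r = 2: 1.25, so the full rate is 25% above the reported one
- r = 3: 1.50, so 50% above
- r = 1: 1.00, no difference
- r = 0.5: 0.875, so 12.5% below

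The direction depends wholly on whether r exceeds 1.

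**4. The collection rules side by side.** Sections 14.4.1 and 14.4.4 turn on a subject being prematurely withdrawn from the study. The Study Definitions page separates ending the study (completion, loss to follow-up, withdrawal of consent, death) from merely stopping therapy. On that reading, a subject who stops the regimen and enters safety follow-up is still in the study, and collection goes on to week 40. But 13.4.2 describes these same subjects as withdrawn from Stage 2, section 10.6 as discontinuing the study, and the notes to the safety follow-up schedules as terminating from it. On that wording the 30-day limit applies. Both readings have textual support, and the protocol does not choose.

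**The case against.** Much can be said for the plan, and most of it limits the point.

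- A reader might infer that every period rate is confined to time on treatment. That is not so. The darTreg period runs from infusion to the end of follow-up, so infused subjects are touched only through the collection conflict.
- Other displays are not limited to treatment. The Safety Sample is analysed as a whole, SAP 8.1.1 reports absolute numbers, SAP 9.2 uses person-time since enrolment, and SAP 9.3 lists deaths, graft losses, Grade 3 or higher infections, severe and chronic rejection, PTLD and malignancies separately. This stands, provided that the events are recorded.
- A reader might take it as settled that AE collection ends 30 days after stopping. The documents support only that two rules conflict. The Study Definitions page and the safety follow-up schedules allow the reading in which collection continues.
- The rejection or infection that leads to stopping happens on treatment and is counted, and stopping under 7.1 is permitted rather than mandatory.
- It is tempting to count all exits at the day 30–44 screen (criteria C1) as removals for rejection or infection. The C1 criteria concern explant pathology, depth of depletion, anticoagulation, biliary obstruction, ALT, steroid taper and HCV, so those exits do not illustrate that mechanism.
- The analyses are descriptive, and the planned precision is low: the Table 8 limits for 4 events in 384 person-weeks differ by a factor of 0.0267/0.0028, about 9.5. A shift of 25% to 50% is small beside that. The stopping rules use counts, not these rates.
- An on-treatment rate is a legitimate description of a regimen.

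The last two items reduce the urgency. They do not remove the mismatch: the stated outcome runs to week 40, the stated IS period rule does not, and no second analysis shows the difference.

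**Conclusion.** The point holds for the Treg-supportive IS period only. A stated rule leaves out later events and weeks of subjects who stop the regimen and are never infused, for reasons that can be outcomes themselves, while the outcome is defined over 40 weeks. Separately, two stated rules for AE collection conflict, and the completeness of the whole-sample analysis depends on which one sites follow.

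The size is not known. Under the assumption of four replaced subjects stopping at week 6, a quarter of the IS person-weeks is lost, and the full rate is 25% to 50% above the reported one if the later rate is 2 to 3 times higher. It would be tempting to conclude that the safety rates are biased downward. The documents do not establish this, because they give no event rate after stopping, and a lower later rate would turn the sign. The plan should be changed because the definition does not match the outcome and the change is cheap.

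**What to change.** 1. In Protocol 15.4.1 and SAP section 5, define the IS period as running from the first Thymoglobulin dose to darTreg infusion, or to week 40 for subjects never infused, whether or not the regimen is stopped. Leave the darTreg period as it is.
2. Keep the on-treatment rate for the IS period as a second line, labelled as such.
3. Reconcile Protocol 14.4.1 and 14.4.4 with 13.4.2 and Appendices 4 and 5, so that AEs belonging to the five safety outcomes are collected to week 40 for everyone who received Thymoglobulin, unless consent is withdrawn. Use one term for stopping therapy and another for leaving the study, in line with the Study Definitions page.

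The cost is a wording change in both documents and some extra AE recording at visits that the safety follow-up schedules already contain. The main IS period rate would then include time off the regimen, which is why the on-treatment rate should stay beside it.

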#### 15.4.2 Analysis of Safety Outcomes

As the safety outcomes are all person-week incidence rates of selected AEs as described in *Section 3.2*, they will be estimated using proportions and exact two-sided 95% confidence intervals in the Safety Sample as a whole and within the two analysis periods defined above.

#### 15.4.3 Supportive Analyses

Since this is a relatively small pilot study, no sub-group analyses, sensitivity analyses or covariate adjustments are planned.

#### 15.4.4 Analyses of Exploratory Outcomes

Mechanistic assays are designed to monitor various Treg cell subset levels over time before and immediately after the initiation of any darTreg infusion. These Treg cell subset measures will be summarized using standard statistical methods for continuous variables and will be displayed graphically by subject over time. The exploratory analyses of the mechanistic outcomes will be described in more detail in the SAP.

Confidential Page 64 of 80

# 15.4.5 Descriptive Analyses

Disposition of subjects will be summarized in the Safety Sample. Reasons for termination of subjects who did not receive whole blood draw or leukapheresis for manufacturing, those who underwent whole blood draw or leukapheresis for manufacturing but did not receive liver transplantation, and those who underwent whole blood draw or leukapheresis for manufacturing and liver transplantation but did not receive any Thymoglobulin or Treg supportive IS will be tabulated.

Standard descriptive statistics for continuous and categorical variables will be used to summarize the following on all subjects in the Safety Sample and for the two analysis periods defined above:

- baseline and demographic characteristics of the subjects
- use of concomitant medications
- reasons for early termination
- all reported AEs

# 15.5 Interim Analyses

No formal interim analyses of this study are planned.

# 15.6 Sample Size Considerations

This pilot study is designed to evaluate 18 subjects through Stage 3 in a modified 3+3 dose escalation design. Therefore, no formal power and sample size analyses have been performed. However, with 18 evaluable subjects undergoing darTreg supportive IS for 12 weeks of follow-up (6 subjects for 40 weeks of follow-up) and up to 12 evaluable subjects undergoing darTreg infusions for 28 weeks of follow-up after infusion, exact 95% confidence intervals on person-week incidence rates will vary in width by analysis period. For example, the following table (*Table 8. Incidence Rates and Confidence Intervals for Selected Numbers of Events and Person-Weeks*) shows incidence rates and confidence intervals for selected numbers of events and person-weeks of 216 (18 subjects x 12 weeks), 336 (12 subjects x 28 weeks), and 384 (6 subjects x 40 weeks + 12 subjects x 12 weeks) in the two analysis periods. It is not known at this time how many subjects may be expected to comprise the entire Safety Sample, which includes subjects who only received leukapheresis.

Confidential Page 65 of 80

Table 8. Incidence Rates and Confidence Intervals for Selected Numbers of Events and Person-Weeks

Number of	Total Person-	Person-Weeks	Lower 95%	Upper 95% Confidence
Events	Weeks	Incidence Rate	Confidence Limit	Limit
2	216	0.0093	0.0011	0.0334
4	216	0.0185	0.0050	0.0474
6	216	0.0278	0.0102	0.0605
8	216	0.0370	0.0160	0.0730
10	216	0.0463	0.0222	0.0851
12	216	0.0556	0.0287	0.0970
14	216	0.0648	0.0354	0.1087
16	216	0.0741	0.0423	0.1203
18	216	0.0833	0.0494	0.1317
20	216	0.0926	0.0566	0.1430
2	336	0.0060	0.0007	0.0215
4	336	0.0119	0.0032	0.0305
6	336	0.0179	0.0066	0.0389
8	336	0.0238	0.0103	0.0469
10	336	0.0298	0.0143	0.0547
12	336	0.0357	0.0185	0.0624
14	336	0.0417	0.0228	0.0699
16	336	0.0476	0.0272	0.0773
18	336	0.0536	0.0317	0.0847
20	336	0.0595	0.0364	0.0919
2	384	0.0052	0.0006	0.0188
4	384	0.0104	0.0028	0.0267
6	384	0.0156	0.0057	0.0340
8	384	0.0208	0.0090	0.0410
10	384	0.0260	0.0125	0.0479
12	384	0.0313	0.0161	0.0546
14	384	0.0365	0.0199	0.0612
16	384	0.0417	0.0238	0.0677
18	384	0.0469	0.0278	0.0741
20	384	0.0521	0.0318	0.0804

Confidential Page 66 of 80

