#### 1.2.5 Rationale for Timing of Treg Administration

Most animal studies of Treg administration have administered Treg at the time of transplantation, in contrast to our study which proposes to give Tregs approximately 12-20 weeks after liver transplant. There are no published studies to our knowledge that have examined the optimal timing for Treg administration. In addition, modeling such studies in animals is difficult due to the variable responses of animals to conventional IS. In addition, the administration of T cell depleting agents often results in long term graft acceptance without further manipulation. Liver transplantation in particular is difficult to model due to the natural tolerogenicity of liver allografts which often require no IS for long-term survival.

We have chosen to delay Treg administration for several reasons. First, in the setting of liver transplantation, the potential for complications is very high, especially early after transplantation. In the context of a safety trial, administering Tregs at the time of transplant would be prohibitively risky. In addition, we expect that the window of T cell depletion after Thymoglobulin® will last at least until the time of Treg administration, 11-20 weeks after liver transplant. Thymoglobulin induction in renal transplant patients induced CD4 depletion out to at least 28 weeks, with no increase in CD4 counts between weeks 12-28 (Tang Q. J., 2012)(See Figure 1). This timing will also allow us to transition eligible subjects to an mTOR-based regimen, which is difficult immediately after liver transplantation for reasons discussed in *Section 1.2.2*. Waiting 11-20 weeks is also beneficial to a safety trial because the incidence of rejection is expected to be lower at that

Confidential Page 22 of 80

time point, allowing a cleaner evaluation of the safety of Treg administration. Delayed administration will also enable us to manufacture darTregs as donor cells are required.

**Figure 1.** Repopulation of CD4+ T cells after Thymoglobuin induction in renal transplant patients. X axis denotes weeks after transplant and Y axis represents Total cell number/ml blood (x  $10^6$ ). Open circles, control arm. Filled circles, thymoglobulin induction arm.

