# **5.4.3** Rationale for Staggering Intervals

All participants in Cohort 1a – those who receive Treg supportive IS alone - must be monitored for 12 weeks prior to enrollment of Cohort 2 and Cohort 1B by the second clinical site. The rationale for selecting 12 weeks is that this interval covers the time period that has the highest incidence of important post-liver transplant complications such as rejection and infection, particularly bacterial and fungal infections related to the transplant operation including those directly related to the transplant incision / wound.

Within each darTreg dosing cohort, there is a mandatory four-week observation period after the administration of darTregs to the 1st patient of each cohort before the 2nd patient can receive darTregs. We have selected a shorter observation time interval for several reasons. First, darTregs will be administered sometime between Week 11-20 after transplant. This is a period of relative clinical quiescence that will readily permit optimal identification of AEs that may be precipitated by the darTreg infusion. Liver transplant recipients have largely recovered from the transplant operation as well as from the baseline liver disease. They continue on anti-viral (until 6 months after transplantation) and anti-

Confidential Page 40 of 80

pneumocystis prophylaxis (until at least 12 months after transplantation) such that the frequency of these infections is very low. Second, we anticipate that the majority of complications associated with darTreg administration (infusion reaction, AR, or infection) are most likely to occur early, soon after administration while the beneficial effect of darTreg administration may well evolve and/or intensify over time. Infection may be precipitated by contamination of the darTreg preparation with infectious agents or with non-donor-alloantigen-reactive Tregs that lead to generalized over-immunosuppression. Similarly, rejection may be precipitated by contamination of the darTreg preparation with T effector cells. In these cases, the deleterious impact of darTreg infusion is expected to manifest soon – within 4 weeks – after infusion. While malignant transformation of infused cells is a concern, the timeframe of this complication as well as its manner of presentation is certainly difficult if not impossible to predict and therefore, this safety concern cannot be mitigated by any sort of mandatory waiting period.

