# 14.5.2.2 Expedited Safety Reporting

This option, with 2 possible categories, applies if the AE is classified as one of the following:

**Category 1**: **Serious and unexpected suspected adverse reaction [SUSAR]** (*Section 14.2.1.1, Suspected Adverse Reaction* and Section 14.2.2, *Unexpected AE* and 21 CFR 312.32(c)(1)i).

The sponsor shall report any suspected adverse reaction that is both serious and unexpected. The sponsor shall report an AE as a suspected adverse reaction only if there is evidence to suggest a causal relationship between the study drug and the AE, such as:

- 1. A single occurrence of an event that is uncommon and known to be strongly associated with drug exposure (e.g., angioedema, hepatic injury, or Stevens-Johnson Syndrome);
- 2. One or more occurrences of an event that is not commonly associated with drug exposure, but is otherwise uncommon in the population exposed to the drug (e.g., tendon rupture);
- 3. An aggregate analysis of specific events observed in a clinical trial (such as known consequences of the underlying disease or condition under investigation or other events that commonly occur in the study population independent of drug therapy) that indicates those events occur more frequently in the drug treatment group than in a concurrent or historical control group.

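### The IS-period rate pools the first 12 weeks after transplant with Cohort 1's weeks 12-40, so it is not comparable with the darTreg-period rate, and no planned rate isolates Cohort 1 after week 12

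*Protocol*

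**What the plan says.** Protocol 15.4 makes the safety analysis descriptive, based on "estimation of person-week incidence rates and their exact two-sided 95% confidence intervals". Protocol 15.4.1 defines two analysis periods, one starting with Thymoglobulin and the IS regimen, the other with darTreg infusion. SAP 5 words the first as "Subjects receive any darTreg supportive IS". In both documents, events and weeks at risk count towards the IS period until infusion and towards the darTreg period from then on. Cohort 1 receives no infusion (Protocol 3.1), so it stays in the IS period to week 40.

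Protocol 15.6 illustrates precision with three person-week totals. Two are 216, from 18 subjects followed for 12 weeks, and 336, from 12 subjects followed for 28 weeks. The third counts Cohort 1 to week 40: "384 (6 subjects x 40 weeks + 12 subjects x 12 weeks) in the two analysis periods". SAP 3 repeats these figures.

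On timing of risk, Protocol 5.4.3 justifies 12 weeks of observation for Cohort 1a because "this interval covers the time period that has the highest incidence of important post-liver transplant complications such as rejection and infection". The same section describes the infusion window as clinically quiet. Protocol 1.2.5 supports later infusion partly because "the incidence of rejection is expected to be lower at that" time point.

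The selected safety outcomes are estimated for the whole Safety Sample and the two periods (Protocol 15.4.2, SAP 8.1.1). Protocol 15.4.3 and SAP 8.1 rule out subgroup, sensitivity and adjusted analyses.

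**The concern.** Two rates with confidence intervals, labelled by treatment, will be read against each other whether or not a test is planned. The IS-period rate carries the high-risk weeks just after transplant; the darTreg rate does not. On the protocol's own account of risk, the darTreg rate should be lower for reasons that have nothing to do with the cells.

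This affects outcomes that can occur in both periods: biopsy-proven rejection, Grade 3 or higher infection, wound complications and cytopenias. The protocol states the direction for rejection and infection, including wound-related infection. For cytopenias I infer it, because Thymoglobulin is given in the first days and Protocol 5.2 names leukopenia and thrombocytopenia as dose-dependent effects. Infusion reactions and other infusion-attributable events cannot arise in the IS period and are not affected.

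In a first-in-human safety study the main risk is masking: a real increase after infusion could sit level with, or below, the pooled IS rate.

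Cohort 1 after week 12 is the follow-up closest in time since transplant to the post-infusion period. Appendix 2 maps its visits to the post-infusion time points, from week 12 as infusion day to week 40 as 28 weeks after infusion. The rate analysis makes no separate use of it.

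**Working it through.** **1. The plan's figures.** All from Protocol 15.6:

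- 18 × 12 = 216
- 12 × 28 = 336
- 6 × 40 + 12 × 12 = 240 + 144 = 384

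The 30 rows of Table 8 reproduce to four decimals with exact Poisson limits: lower = χ²(0.025; 2x)/(2T), upper = χ²(0.975; 2x+2)/(2T). For example, 2/216 gives 0.0093 (0.0011, 0.0334).

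**2. Content of the 384.** Weeks 0-12: 216, or 216/384 = 56.25%. Cohort 1 weeks 12-40: 6 × 28 = 168, or 43.75%.

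**3. Ratio expected with no darTreg effect.** Let k be the event rate in weeks 0-12 divided by the rate afterwards. The documents give only its direction (above 1), so its size is an assumption. I take a step change at week 12 and the late rate throughout the darTreg period.

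- Infusion at week 12: IS-period rate = (216k + 168)/384 times the late rate, so the apparent ratio of darTreg to IS rate = 384/(216k + 168).
- Infusion at week 20, the end of the allowed window: IS person-weeks = 12 × 20 + 6 × 40 = 480, of which 216 are early and 264 late. Apparent ratio = 480/(216k + 264).
- Against the 216 first-12-week person-weeks alone: apparent ratio = 1/k.

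| k (assumed) | Infusion week 12 | Infusion week 20 | Against weeks 0-12 only |
|---|---|---|---|
| 1 | 1.00 | 1.00 | 1.00 |
| 2 | 384/600 = 0.64 | 480/696 = 0.69 | 0.50 |
| 3 | 384/816 = 0.47 | 480/912 = 0.53 | 0.33 |
| 4 | 384/1032 = 0.37 | 480/1128 = 0.43 | 0.25 |

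**4. Masking.** With infusion at week 12, a true post-infusion rate ratio of (216k + 168)/384 would appear as 1.0. That is 1.56, 2.13 and 2.69 for k = 2, 3 and 4.

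**5. After the split.** Cohort 1 weeks 12-40 (168 person-weeks) against the darTreg period (336) has an expected ratio of 1.0 for any k, if timing is the only difference. If all infusions were at week 20 and follow-up ended at week 40, the time-matched person-weeks would be 6 × 20 = 120 and 12 × 20 = 240.

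**6. Precision.** 2/168 = 0.0119, exact 95% CI 0.0014 to 0.0430. For 2/168 against 4/336 the rate ratio is 1.0. Conditional on six events, the exact interval for the infused share of 4/6 is 0.2228 to 0.9567. Converting by p/(1−p) × 168/336 gives 0.14 to 11.05.

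**The case against.** The strongest reply is that the plan makes no such comparison. The outcomes are descriptive and "no formal power and sample size analyses have been performed". No section contrasts the two periods or calls Cohort 1 a control for clinical events; its stated safety role is a staggered lead-in. That stands, and it limits the point to how results are presented and read.

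A reader might infer that Cohort 1's later experience disappears from the report. The documents do not support this. SAP 9.2 tabulates adverse events by cohort and by study stage, SAP 9.3 gives separate displays for the serious outcomes, and SAP 9.5.3 summarises biopsies by cohort and timepoint. By-cohort tables compare like with like over the planned 40 weeks, but they give counts and percentages with the first 12 weeks included. The SAP 9.2 incidence rate divides by person-time since enrolment, which starts before transplant. None supplies a selected-outcome rate for Cohort 1 after week 12.

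A reader might also infer that darTreg is bound to come out ahead, or that the reference to a control group in Protocol 14.5.2.2 turns the period rates into a causal comparison. Neither follows. The size of k is unknown and chance variation in a trial this small is large; 14.5.2.2 is a criterion for expedited reporting and does not mention these rates.

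Table 8 does list 216 person-weeks separately. But 15.4.1 defines no period ending at week 12, and setting that rate against the darTreg rate widens the gap to 1/k.

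Finally, splitting does not make the groups equivalent. Infused subjects must pass Screen D (Protocol 4.3.5), which excludes rejection on biopsy, raised ALT and detectable EBV or CMV DNA, among others; Cohort 1 has no such gate, which favours the infused group. Infused subjects also have a protocol biopsy one week after infusion (Protocol 8.3) that Cohort 1 lacks, which raises detection of rejection. Both objections stand and belong in the report as caveats.

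**Conclusion.** The point holds as a defect in how the analysis periods are defined. For rejection, Grade 3 or higher infection, wound complications and cytopenias, the pooled IS-period and darTreg-period rates are not comparable. The direction of the distortion follows from the protocol's statements about risk over time. Its size rests on an assumed early-to-late ratio of 2 to 4, a step at week 12 and the same k for each outcome: an apparent ratio of 0.64 to 0.37 with infusion at week 12, or 0.69 to 0.43 at week 20, with no true effect. The data to correct this are already collected at aligned visits. It is worth changing, but it is not an error in a planned test, and the corrected display will be imprecise.

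**What to change.** In Protocol 15.4.1 and SAP 5, split the IS period at a fixed week 12. Do not use the median infusion week, which depends on the data. Report the selected outcomes as:

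- (a) all Thymoglobulin-treated subjects, to week 12 or infusion, whichever comes first;
- (b) Cohort 1 from week 12 to week 40, with any time in Cohorts 2-4 after week 12 and before infusion shown separately;
- (c) infused subjects after infusion.

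Show (b) beside (c) descriptively, without a test. State in the text that:

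- the pooled IS-period and darTreg-period rates are not comparable;
- (b) has only about 168 person-weeks, with the interval of 0.14 to 11.05 above as an example of its precision;
- Screen D selection and the one-week post-infusion biopsy remain as differences between (b) and (c).

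The cost is wording in two sections and a few extra table columns. No new visits, samples or subjects are needed. The protocol wording needs the amendment approvals in Protocol 18.1, so it can go with the next amendment.
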